#### 1.3.3.4. Phase II pediatric trial of RTS,S/AS02D; Bridging Study (Malaria-034)

Malaria-034 was a phase I/II randomized double-blind bridging study to evaluate the safety and immunogenicity of 3 doses of GlaxoSmithKline Biologicals' candidate vaccine RTS,S/AS02D (0.5 mL dose) in comparison to 3 doses of the existing formulation RTS,S/AS02A (0.25 mL dose) administered to children aged 3 to 5 years living in a malaria-endemic region of Mozambique. Both vaccines contain the same constituents but the final volume was adjusted to be compatible with existing EPI practices.

Two hundred children were enrolled into two groups of 100 subjects each, of which 189 (93 of whom received RTS,S/AS02D [D group] and 96 received RTS,S/AS02A [A group]) subjects were included in the ATP analysis of safety and reactogenicity and 143 (67 and 76 subjects respectively) subjects in the analysis of immunogenicity.

The safety profile of the two vaccine formulations was similar. Solicited symptoms were as shown in Table 14, with pain the more frequent local symptom and fever the most frequent general symptom reported. Symptoms were generally mild to moderate in intensity, and decreased in frequency with subsequent doses.

Unsolicited symptoms were reported following 69 (24.7%) doses in the RTS,S/AS02D group and following 56 (19.4%) in the RTS/SAS02A group. The most frequently reported symptoms were malaria (18% of the subjects in the D group and 25% in the A group) and upper respiratory tract infection (14% of the subjects in the D group and 12% in the A group). An unsolicited symptom, injection site erythema, deemed to be related to vaccination was reported for a single subject, following one dose in the D group. Three

symptoms in the D group and 8 in the A group were graded 3 in intensity, none of which were related to vaccination.

One serious adverse event occurred in a subject in the A group. This subject had severe malaria which lasted 4 days and required hospitalization. The subject recovered and the event was deemed by the investigator to be unrelated to vaccination.

Group		R	S,S/AS02D	) (N = 93)		R	TS,S/AS02	A (N = 96)	
		n	%	95	% CI	n	%	95%	6 CI
Pain	Any	31	33.3	23.9	43.9	43	44.8	34.6	55.3
	Grade 3	2	2.2	0.3	7.6	1	1.0	0.0	5.7
Swelling	Any	8	8.6	3.8	16.2	23	24.0	15.8	33.7
Ū	Grade 3	1	1.1	0.0	5.8	4	4.2	1.1	10.3
Drowsiness	Any	12	12.9	6.8	21.5	8	8.3	3.7	15.8
	Grade 3	2	2.2	0.3	7.6	1	1.0	0.0	5.7
Fever	Any	26	28.0	19.1	38.2	25	26.0	17.6	36.0
	Grade 3	6	6.5	2.4	13.5	3	3.1	0.6	8.9
Irritability	Any	11	11.8	6.1	20.2	3	3.1	0.6	8.9
	Grade 3	3	3.2	0.7	9.1	1	1.0	0.0	5.7
Loss of	Any	15	16.1	9.3	25.2	14	14.6	8.2	23.3
Appetite	Grade 3	0	0.0	0.0	3.9	0	0.0	0.0	3.8

# Table 14: Incidence of any and grade 3 local and general solicited symptoms inthe 7-day follow-up after vaccination

For each dose and overall/subject: 95%CI = Exact 95% confidence interval

N = number of subjects having received at least one dose

n/% = number/percentage of subjects reporting a specified symptom

Grade 3 injection site pain; cries when limb is moved/spontaneously painful.

Grade 3 swelling; > 20 mm.

Fever: axillary body temperature  $\geq$  37.5°C.

Grade 3 fever; axillary body temperature  $\geq$  39.0°C.

Grade 3 drowsiness; drowsiness that prevents normal activity.

Grade 3 loss of appetite; not eating at all.

Grade 3 irritability/fussiness; crying that cannot be comforted/prevents normal activity

Non-inferiority of the RTS,S/AS02D vaccine formulation was proven with respect to the immune response elicited. Table 15 shows the anti-CS seropositivity rates and GMTs one month following the third vaccine dose and Table 16 gives the ratios of post vaccination GMTs. All subjects in both groups were seropositive for anti-CS antibodies one month following the third vaccine dose. The RTS,S/AS02A:RTS,S/AS02D GMT ratio was 0.9 (clinical limit of non-inferiority: upper limit of 95% CI = 3).

# Table 15Seropositivity rates and geometric mean titers (GMT) for anti-CS
antibody titers one month after Dose 3 (ATP cohort for
immunogenicity)

Group	Ν		≥ 0.5	EU/mL			GMT		MIN	MAX
				95	% CI	Value	9 5%	6 CI		
		n	%	LL	UL		LL	UL		
RTS,S/AS02D	67	67	100.0	94.6	100.0	190.9	150.3	242.4	14.3	1314.3
RTS,S/AS02A	76	76	100.0	95.3	100.0	179.6	145.9	221.0	16.3	1276.9

N = number of subjects with available results

GMTs calculated on all subjects

EU/mL: ELISA units per mL

n/% = number/percentage of subjects with titer within the specified range

95% CI = 95% confidence interval; LL = Lower Limit; UL = Upper Limit

MIN/MAX = Minimum/Maximum

PRE = pre-vaccination

PIII (M3) = Post dose 3 Month 3

# Table 16 Ratios of post-vaccination anti-CS GMT at PIII (M3) between Group A and Group D with their 95% CIs (ATP cohort for immunogenicity)

Antibody	RTS	s,S/AS02A	RTS	S,S/AS02D	-	Ratio oup A/Group D)			
	Ν	GMT	Ν	GMT	GMT ratio	ç	5% CI		
						LL	UL		
ANTI-CS	76	179.6	67	190.9	0.9 0.7 1.3				

N: Number of subjects with available results

95% CI LL, UL: 95% lower and upper confidence interval limits (ANOVA model)

All subjects were seroprotected with respect to anti-HBs after vaccination, as shown in Table 17, and GMTs exceeded 17 000 mIU/ml in both groups. The

RTS,S/AS02A/RTS,S/AS02D ratio of post-vaccination anti-HBs GMTs (Table 18), and adjusted ratio were 0.7 and 0.8 respectively (clinical limit of non-inferiority: upper limit of 95% CI = 3).

# Table 17Seroprotection rates and geometric mean titers (GMT) for anti-HBs
antibody titers one month after dose 3 (ATP cohort for
immunogenicity)

Group	Ν		≥ 10 ı	mIU/ML			GMT		MIN	MAX
				959	% CI	Value	9 5%	6 CI		
		n	%	LL	UL		LL	UL		
RTS,S/AS02D	67	67	100.0	94.6	100.0	23977.6	17895.5	32126.9	984.9	446880.0
RTS,S/AS02A	76	76	100.0	95.3	100.0	17410.0	13322.3	22751.9	1264.5	823500.0

N = number of subjects with available results

GMTs calculated on all subjects

 $n/\!\%$  = number/percentage of subjects with titer within the specified range

95% CI = 95% confidence interval; LL = Lower Limit; UL = Upper Limit

MIN/MAX = Minimum/Maximum

PRE = pre-vaccination

PIII (M3) = Post dose 3 Month 3

# Table 18Ratios of post-vaccination anti-HBs GMT at PIII (M3) between Group
A and Group D with their 95% CIs (ATP cohort for immunogenicity)

Antibody	RTS,S/AS02A		RTS,S/AS02D		Ratio (Group A/Group D)		
	Ν	GMT	Ν	GMT	GMT ratio	959	% CI
						LL	UL
Anti-HBs	76	17410.0	67	23977.6	0.7	0.5	1.1

N: Number of subjects with available results 95% CI LL, UL: 95% lower and upper confidence interval limits (ANOVA model)

#### 1.3.4. Concurrent protection against hepatitis B

The hepatitis B surface antigen (HBsAg) contained in the RTS,S candidate malaria and hepatitis B vaccine is encoded by the hepatitis B virus S protein gene that is identical to the gene used to express HBsAg in GSK Biologicals' Engerix-B vaccine against hepatitis B.

Non-inferiority of the HBsAg response of RTS,S/AS02A compared to the licensed vaccine Engerix-B has been formally demonstrated in the study Malaria-026 [Alonso, 2004] (refer to Section 1.3.3.3). The RTS,S/AS02D vaccine has been shown to induce high levels of seroprotection and titers in the study Malaria-034 (refer to Section 1.3.3.4)

# 1.4. Rationale for the study design

There are two reasons why the RTS,S/AS02D candidate malaria and hepatitis B vaccine is being developed for delivery through the infant Expanded Program on Immunization (EPI) of the World Health Organization (WHO). Firstly, the vaccine is being developed to prevent severe malaria disease which occurs from about 4 months of age coinciding with the time that maternally-acquired immunity wanes [Snow 1990, Snow 1994]. Secondly the EPI has been highly successful at increasing the coverage of basic vaccines across the developing world. With the goal of integration into the EPI infant regimen, a 0, 1, 2 month schedule has been evaluated in children and the final dose volume has been adjusted to 0.5 mL to be compatible with the standard syringes used by EPI (see Section 1.3.2).

Although RTS,S/AS02D is primarily being developed as a vaccine against malaria, the particles of RTS,S contain HBsAg and the vaccine induces high seroprotection rates against hepatitis B (see Section 1.2.2). Therefore it is logical to propose that, in malaria endemic regions, RTS,S/AS02D replaces the existing hepatitis B vaccine in the infant regimen. This approach has the advantage that adding malaria immunization to the EPI schedule requires no extra vaccination clinic visits in the first year of life, which is more practical for parents and EPI services.

As the next step in the development path, this study examines the feasibility of giving RTS,S/AS02D to infants in the EPI age range; three doses of RTS,S/AS02D will be given at 10, 14 and 18 weeks of age, staggered with the administration of DTPw/Hib at 8, 12 and 16 weeks of age. The control arm will receive Hepatitis B vaccine at the times RTS,S/AS02D is given. As this is the initial assessment of vaccine safety in infants, the conduct of this study will precede studies of the coadministration of RTS,S/AS02D with

EPI vaccines. In this study, the licensed vaccines used are Engerix-B® (GlaxoSmithKline Biologicals) and TETRActHibTM (Aventis Pasteur).

Because this is an experimental regimen of hepatitis B immunization, infants at high risk of hepatitis B infection will be excluded from the trial. Infants born to women who are chronic carriers of hepatitis B virus (HBV) will receive the licensed vaccine in a regimen starting at birth (refer to Section 5.1.10.2.1).

Infants who are born to mothers who test positive for HIV will not be enrolled in the trial. HIV positive children may not respond normally to standard EPI vaccines and thus interfere with the analysis of immunogenicity in this study [Ryder et al 1993]. Also the high morbidity experienced by HIV positive children may obscure safety patterns.

Oral polio vaccine (OPV) will be administered according to local medical practice (birth, 8, 12, 16 weeks co-administration with other EPI vaccines) and will not be administered as part of this protocol. Antibody titers to OPV will not be assessed as part of this protocol but will be evaluated in Phase 3 development.

### 1.4.1. Safety monitoring plan

This study is the first administration of RTS,S/AS02D to infants and therefore a detailed safety plan, overseen by a formally constituted Data Safety Monitoring Board (DSMB) operating under a charter, is implemented (the role of the DSMB is fully detailed in Section 5.1.3). The DSMB is empowered to temporarily suspend the trial on the basis of any safety concern or meeting predefined criteria for temporary suspension (Section 5.1.6).

The rate of enrolment is uncertain as it is dependent on the birth rate, and could range from 6 to 12 months. The DSMB will receive all SAEs within 24 hours. In addition, the DSMB will review summarized safety and reactogenicity data at protocol-defined timepoints, so that enrollment to the trial could be halted in a timely fashion if a safety issue was detected (refer to Section 5.1.5).

#### 1.4.1.1. Safety data collection on TETRActHib

Comprehensive safety data on the licensed vaccine TETRActHib will be collected under this protocol in an open fashion. This data that is collected in the same children, at the same time, by the same methodology as the data on RTS,S/AS02D will provide a useful bench mark in the interpretation of reactogenicity of RTS,S/AS02D.

## 1.4.2. Assessment of proof of concept

Prior to initiating definitive studies of vaccine efficacy in infants that will require larger sample sizes, the minimum number of infants will be enrolled in this study to achieve proof-of-concept of vaccine efficacy. Proof-of-concept will be assessed as time-delay to first infection with asexual forms of *P. falciparum*.

The time to infection was assessed following homologous challenge in the challenge model conducted at the WRAIR; estimates of vaccine efficacy with RTS,S/AS02 in field trials were consistently approximately 40% [Malaria-026, Malaria-005]. When the vaccine was evaluated under conditions of natural exposure in The Gambia [Malaria-005], the vaccine efficacy for the time to first infection in adults was 34% (CI 8.0% to 53.0%). The recently conducted Phase 2b trial in Mozambican children (Malaria-026) was the first study in which both clinical and parasitological endpoints were assessed. Measured concurrently in two groups of children, vaccine efficacy against first clinical episode was 30% (95% CI: 11.0% to 44.8%) and against first infection was 45% (95% CI: 31.4% to 55.9%).

Time to first infection will be used to assess proof-of-concept in infants, because it has proven to be consistent when measured by different methodologies in different populations and because, in the recent Malaria-026 study, the point estimate of efficacy against infection was consistent with the estimate of prevention of clinical episodes.

#### **1.5.** Rationale for studying the determinants of vaccine response

Molecular techniques provide the means to address the problems of individual and group variations in specific vaccine responses, and to gain further insight into the general mechanisms of response to vaccines. These technologies have recently undergone substantial development and are now able to successfully dissect the mechanisms in human disease.

This study of the response to malaria vaccination will examine two types of genes. The first group would be candidate genes known to be important in inflammatory or immunological responses to infection with malaria and these should be investigated with respect to the potential effects of variations in these genes. Candidate genes specific for malaria vaccination responses would include genes that: (1) are known to be directly involved in infection with malaria; (2) have common polymorphisms that affect the amount or function of the protein produced by the gene; or (3) are related to a specific marker of infection with malaria. A list of potential candidate genes is provided below (Table 19). To date, there have been no reports examining the role of these or other polymorphisms on response or non-response to malaria vaccines. The second group of genes are those along the immunological pathways that are most likely to be important in protection from infection and the most obvious of these are the Th1/Th2 immune response pathways. Indeed, at the early time of life that vaccination is given, there is a general delay in establishment of Th1 responses and the initial response to vaccine antigens is initially strongly Th2 biased [Rowe, 2000]. A list of genes that are directly or indirectly involved in Th1/Th2 responses is provided below (Table 19).

Candidate genes for malaria infection	Genes involved directly or		
	indirectly with Th1/Th2 immunity		
Intercellular adhesion molecule 1 (ICAM-1)	Gly241Arg, Glu469Lys		
IL-10	1082G/A, 819C/T, 592C/A		
CD36	14T/C, 53G/T, 1439G/C		
CD14	159C/T, 1359G/T, 1145A/G		
Inducible nitric oxide synthase (iNOS)	1173C/T		
H4	<del>1098T/G, 589C/T, 33C/T</del>		
Complement receptor 1 (CR1)	3650A/G		
IL-4R alpha	IIe50Val, GIn551Arg, Ser478Pro		
Mannose binding protein (MBP)	Gly54Asp, Gly57Glu		
<del>IL-13</del>	1111C/T, Arg130Gln, 4738G/A		
Tumor necrosis factor alpha (TNF alpha)	308G/A		
TLR4	2026A/T, 1607T/C, Asp299Gly, Thr399lle		
Toll-like Receptor (TLR2)	Arg677Trp, Arg753Gln		
IL-1beta	511C/T, 3953C/T		
IL-6	<del>174G/C, 572G/C</del>		
<del>IL-12B</del>	1188A/C		
IFN gamma receptor 1 (IFN gamma R1)	56T/C		

#### Table 19 Candidate genes for determinants of vaccine response study

A blood sample for the determination of determinants of vaccine response will be taken during this trial (see Section 5.3) and analyzed according to CISM SOP.

(Amended 12 April 2005).

#### **1.6.** Rationale for testing cell-mediated immunity

RTS,S/AS02A has been shown to be a powerful inducer of antigen-specific humoral and CMI response in preclinical and clinical studies [GSK data on file, Malaria Investigator's Brochure 2003]. The RTS,S/AS02D vaccine is believed to elicit a strong neutralizing humoral immune response directed against surface-exposed sporozoite proteins, and elicit CMI responses characterized by predominantly CD4+—Th1 cells, that are hypothesized to either destroy infected hepatocytes and/or limit intracellular parasite development through appropriate cytokines.

CMI response induced by a vaccine antigen formulated in AS02 adjuvant has never before been measured in infants. As it is believed to be a key component in protecting vaccinees against the *P. falciparum* parasite it will be measured in this trial. We will compare the CMI response of infants vaccinated with RTS,S/AS02D against the response of infants vaccinated with Engerix-B prior to vaccination, one month post Dose 3 and 3 months post Dose 3. The characterization of the specific CMI response will be performed as exploratory readouts and will address the most appropriate cellular markers.

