# Endpoint assessed at screening, 1 month post Dose 3 and 3/2 months post Dose 3 of Engerix-B or RTS,S/AS02D

• The frequency of CS-specific CD4+ and CD8+ T cells, as measured by intracellular cytokine staining.

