#### 10.6.4. According to protocol (ATP) cohort for analysis of efficacy

The ATP cohort for analysis of efficacy will include all evaluable subjects (i.e. those meeting all eligibility criteria, complying with the procedures defined in the protocol, with no elimination criteria during the study) for whom data concerning efficacy endpoint measures are available.

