# 10.9.2. Analyses of immunogenicity

The primary analysis will be based on the ATP cohort for analysis of immunogenicity. If the percent of enrolled subjects excluded from this ATP cohort is more than 5%, a second analysis based on the Total Vaccinated cohort will be performed to complement the ATP analysis.

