#### 10.9.4. Exploratory analysis

The exploratory endpoints will be analyzed in the Total Vaccinated Cohort and the ATP Cohort for efficacy.

For the first exploratory endpoint (time to the first clinical episode of symptomatic *P*. *falciparum* malaria defined as the presence of *P*. *falciparum* asexual parasitemia above 500 per  $\mu$ L on Giemsa stained thick blood films AND the presence of fever [axillary temperature  $\geq 37.5^{\circ}$ C] at the time of presentation), the time at risk is defined as in Section 10.9.3.1. However, the time at risk will begin at Day 0 and no adjustments will be made for the absences from the study area and the anti-malarial drug therapy. Vaccine efficacy will be calculated in the same manner as described in Section 10.9.3.2 using Cox regression models. Only crude estimates, not adjusted for prognostic/stratifying factors will be presented.

This analysis will be done including cases from the passive case detection only (see Section 5.1.16) and including cases from both the passive case detection and the active detection of infection (ADI, see Section 5.1.17)

Note that the total number of clinical episodes will only be analyzed at the end of the single-blind phase.

The frequency of CS-specific CD4+ and CD8+ T cells will be summarized for each group at each timepoint (descriptive statistics).

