## **Rationale/background for changes:**

The CISM, GSK Biologicals and MVI teams have decided to remove assessment of Determinants of Vaccine Response from this study. All references to the assessment have been removed throughout the protocol.

In order to ensure that there is sufficient blood available to carry out Cell-Mediated Immunity assessment at protocol-defined timepoints it is necessary to raise the amount of blood to be collected at these timepoints from 1 mL to 2 mL. The sampling methodology is not specified per-protocol but is clarified in the informed consent documents.

A further elimination criterion has been added in order to ensure that children who fail to thrive will not receive experimental vaccine.

In order to assess the pertussis response it is necessary to account for maternally acquired immunity. Assessment of antibodies to pertussis at screening was omitted in previous versions of the protocol. This has been corrected in this amendment.

Text and a table have been added to help clarify the time periods between which different classes of oncomitant medications/treatments must be recorded.

A number of typographical errors that have been noticed since the previous amendment was finalized have been corrected in this version

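### The protocol says it will compare T-cell responses between arms but plans only per-group summaries, and it ties the per-protocol analysis of this immune endpoint to the efficacy cohort

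*Protocol*

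**What the plan says.** Section 1.6 gives the intent: "We will compare the CMI response of infants vaccinated with RTS,S/AS02D against the response of infants vaccinated with Engerix-B prior to vaccination". The same sentence adds one month and three months after Dose 3 as further times of comparison. It also sets the status of the work: "The characterization of the specific CMI response will be performed as exploratory readouts". Section 10.4 lists the frequency of CS-specific CD4+ and CD8+ T cells among the exploratory endpoints, at screening and at two times after Dose 3.

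Section 10.9.4 fixes the analysis: "The frequency of CS-specific CD4+ and CD8+ T cells will be summarized for each group at each timepoint (descriptive statistics". The same section sets the populations: "The exploratory endpoints will be analyzed in the Total Vaccinated Cohort and the ATP Cohort for efficacy". Section 10.6.4 defines the second of these as evaluable subjects "for whom data concerning efficacy endpoint measures are available". For antibody responses, including anti-CS at Visit 11, Section 10.9.2 says: "The primary analysis will be based on the ATP cohort for analysis of immunogenicity".

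Amendment 2 (Appendix H) explains that it was necessary "to raise the amount of blood to be collected at these timepoints from 1 mL to 2 mL" so that enough blood would be available for CMI. Section 5.4 applies this at Visits 1, 10 and 11.

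**The concern.** Two things do not fit together.

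First, the stated intent is a comparison of the vaccines, but the planned output is two columns of summary statistics. A reader will see a difference between the columns without any measure of its precision. Section 1.6 describes CMI as a likely key part of protection, not previously measured in infants for an antigen given with this adjuvant. The sampling burden on the infants was raised to obtain it. A stated comparison should end in an estimate.

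Second, the only per-protocol set named for this immune endpoint is selected on efficacy data. Whether an infant has usable efficacy data says nothing about whether the T-cell sample is valid. The selection also happens after randomization and may be affected by vaccine assignment. The per-protocol summaries of T cells and of anti-CS, taken from the same infants at the same visits, would then rest on sets that differ for no immunological reason.

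**Working it through.** The protocol gives no sample size, SD or effect size for CMI, so there is no figure to reproduce. The point rests on the text; the arithmetic is for scale only.

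**1. Intent against analysis.** Section 1.6 announces a between-arm comparison at three times. Section 10.9.4 provides a per-group summary at each time and no difference, interval or model. Elsewhere the protocol writes out a between-arm estimate when it wants one: the difference in seroprotection rates with a 95% CI (10.8.3.1) and the difference in geometric mean parasite density with a 95% CI (10.9.3.2). For CMI it specifies the analysis and stops at description.

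**2. Choice of set.** Section 10.6.3 defines an ATP immunogenicity cohort by availability of immunogenicity data. Sections 10.8.3 and 10.9.2 use it for anti-CS. Section 5.4 and Table 23 show anti-CS and CMI drawn together at Visits 10 and 11. Section 10.9.4 assigns CMI to the efficacy cohort instead.

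**3. Who may differ between the sets.** Randomization is at Visit 2 (Day 0). Blinded vaccine is given on Days 14 and 44, and the clearance slide is taken at Visit 8 (Day 74). Under Section 5.1.17, slide-positive infants leave the active surveillance and do not count for the proof-of-concept endpoint. They therefore probably fall outside the ATP efficacy cohort, although Section 10.6.4 does not say so.

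The slide-positive rate is not given. A rough guide uses the highest district survey prevalence in Section 4.1.3 (34.0%) and the clinical responses in Section 4.1.5.4 (83% for sulfadoxine-pyrimethamine, 93% for amodiaquine). It assumes that a slide is positive only when treatment has failed:
- Failure as for sulfadoxine-pyrimethamine alone: 0.34 × 0.17 = 0.058.
- Failure as for amodiaquine alone: 0.34 × 0.07 = 0.024.

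That is about 2 to 6 infants per 100. Both drugs are given together, which should lower it. Transmission at Ilha Josina was higher than at Manhiça (1.3.3.3.1), and clinical response is not parasite clearance, either of which could raise it. A loss of 15% at the 17% failure rate would need a prevalence of 0.15 / 0.17 = 88%.

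**4. What a between-arm estimate would give.** Assume a two-sided 95% interval, equal arms and a response in SD units. The half-width is 1.96 × √(2/n):
- n = 100 per arm: 1.96 × √0.02 = 0.28 SD.
- n = 60 per arm: 1.96 × √(1/30) = 0.36 SD.

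The 100 per arm is the evaluable number that Section 10.5.2 uses for anti-HBs. It is an upper guide here, because CMI has the lowest assay priority at each visit in Table 23.

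**5. What the screening value could add.** With the screening value as covariate, residual variance is multiplied by 1 − ρ², where ρ is its correlation with the later value. At n = 100 per arm, starting from 0.277 SD, the half-width is:
- ρ = 0.1: 0.277 × √0.99 = 0.276 SD.
- ρ = 0.3: 0.277 × √0.91 = 0.264 SD.
- ρ = 0.5: 0.277 × √0.75 = 0.240 SD.
- ρ = 0.7: 0.277 × √0.51 = 0.198 SD.

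The protocol gives no ρ. If screening frequencies are near zero, the gain is likely to be small. A change score would be a poor substitute: its variance factor is 2(1 − ρ), which is 1.8 at ρ = 0.1 and 1.4 at ρ = 0.3.

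**The case against.** The strongest reply is that description suits the declared status. CMI is an exploratory readout, Section 2 has no CMI objective, and side-by-side summaries are an informal comparison. Anti-CS, a secondary endpoint, is also only described per group. A separate reporting and analysis plan is announced in Section 6.5 and could add a contrast. Much of this stands, and it rules out calling the gap serious. It does not remove it. The anti-CS objective in Section 2.2 is itself to describe, so its analysis matches its aim; Section 1.6 sets a different aim for CMI. Exploratory status argues against formal testing, not against an estimate with an interval. The protocol is also not silent here, because it states the analysis and the sets.

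A reader might infer more than the text supports:
- *A comparison from baseline was promised.* It was not. Pre-vaccination is one of three times of comparison, not a reference for change.
- *The baseline goes unused.* It does not. Screening is a CMI timepoint and is summarized for each arm.
- *T-cell data of slide-positive infants disappear from the report.* They do not. The Total Vaccinated Cohort is named as well and keeps them. Anti-CS is also reported in that cohort if more than 5% of subjects fall outside its ATP set, so the two can be read together there.
- *Slide-positive infants are excluded from the ATP efficacy cohort by rule.* This is an inference. The exploratory clinical malaria endpoints run from Day 0 and still apply to these infants.
- *Three months in Section 1.6 contradicts 3½ months in Section 10.4.* This is rounding; Section 5.1.14.2 describes Visit 11 as about three months after Dose 3.

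**Conclusion.** The point holds in a limited form. The comparison announced in Section 1.6 has no planned estimate or interval, and the per-protocol set for an immune endpoint is defined by efficacy data although an immunogenicity cohort exists and serves anti-CS from the same visits.

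It is minor. No primary or secondary conclusion is affected. The omitted estimate would have had a half-width of about 0.28 SD with 100 infants per arm, or 0.36 SD with 60; both sample sizes are assumptions for CMI. The two ATP sets probably overlap heavily. The rough guide of 2 to 6 infants per 100 rests on prevalence and treatment figures not measured in this population, and on the inferred exclusion of slide-positive infants. The case for the immunogenicity cohort does not depend on that number, because efficacy-data availability is the wrong criterion for a T-cell result whatever the rate.

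**What to change.** In Section 10.9.4:
- Name the ATP immunogenicity cohort as the per-protocol set for CS-specific CD4+ and CD8+ frequencies, and keep the Total Vaccinated Cohort as support.
- At Visits 10 and 11, report the RTS,S/AS02D versus Engerix-B difference in each frequency with a 95% CI, labelled exploratory and without formal testing. The scale can be left to the reporting and analysis plan.
- Keep the per-group summary at screening. That sample precedes randomization, so a difference there carries no treatment effect.
- Treat adjustment for the screening frequency as an optional sensitivity analysis. Its gain depends on an unknown correlation. CMI ranks last of four assays at screening and Section 10.7 does not replace missing immunogenicity values, so infants without a screening result should stay in the unadjusted estimate.

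The cost is a wording change and a little more analysis work on an exploratory endpoint. No extra sample, visit or assay is needed.
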